Comparing Through-the-Needle with Suture-Method Catheter Designs for Popliteal Nerve Blocks

NCT03442036

Principal Investigator: [name], MS

Date of registration: February 22, 2018

Research Protocol

This parallel group study adhered to Good Clinical Practice quality standards and ethical guidelines defined by the Declaration of Helsinki. Study protocol approval as well as data and safety oversight were conducted by the University of California San Diego Institutional Review Board (IRB #170834; San Diego, California). Written, informed consent was obtained from all subjects participating in the trial.

Enrollment was offered to all adults who met study criteria undergoing painful unilateral ambulatory foot and/or ankle surgery with a planned popliteal-sciatic perineural catheter for postoperative analgesia at a single institution. Exclusion criteria included:

1. Clinically-apparent neuropathy in the surgical extremity
2. Chronic high-dose opioid use (defined as daily use for more than 4 weeks prior to surgery of at least the equivalent of 20 mg oxycodone);
3. History of opioid misuse
4. Surgery outside of ipsilateral sciatic and saphenous nerve distributions (e.g., iliac crest bone graft)
5. Patients with nerves deeper than 5 cm from the skin surface

6. Pregnancy
7. Inability to communicate with the investigators and hospital staff
8. Incarceration.

Patients eligible for the study were called the night before surgery by one of the investigators to offer enrollment. If not available by telephone, patients were offered enrollment in person by one of the investigators prior to block placement if there was sufficient time to fully discuss the study and answer all questions. Only one patient who was offered enrollment in the study declined.

Pre-operative Procedures. After applying standard ASA monitors, oxygen by facemask, and positioning the patient prone, intravenous midazolam and fentanyl were titrated for patient comfort while ensuring patients remained responsive to verbal cues. A 13 to 6 MHz 38-mm linear array ultrasound transducer (Edge II; SonoSite, Bothell, WA) was used to visualize the sciatic nerve 5 cm proximal to the bifurcation with a short-axis view. After confirming this site was appropriate for catheter insertion, the subjects were randomized using a computer-generated list in opaque, sealed envelopes to one of two treatments groups (1:1 ratio) in blocks of 4:

1. Through-the-needle [“Traditional” group]
2. Suture-catheter [“Suture” group]

The catheter site was sterilely prepped, draped, and the needle entry site anesthetized with lidocaine 1% (3 mL).

Through-the-needle insertion: A 17-gauge Tuohy needle (FlexTip Plus; Teleflex Medical, Research Triangle Park, NC) was inserted on the posterior aspect of the leg, from lateral to

medial, using an in-plane, short-axis ultrasound-guided technique. Normal saline (5-10 mL) was used to hydrodissect around the sciatic nerve to facilitate catheter insertion. A 19-gauge flexible, single-orifice perineural catheter was inserted under ultrasound guidance. Correct location of the tip was confirmed by injection of normal saline (1-2 mL) with visualization of spread adjacent to the nerve. The catheter was then secured with clear, occlusive dressings. To facilitate tourniquet placement in the operating room, the catheter was taped up the lateral thigh and secured on the lower abdomen.

Suture-catheter insertion: A short-beveled 19-gauge suture needle (75 mm radius, 160 mm length) joined to a 19-gauge, single-orifice, nylon catheter (Certa Catheter, Ferrosan Medical Devices, Szczecin, Poland) was inserted on the posterior aspect of the leg, from lateral to medial, under ultrasound guidance using an in-plane technique. Normal saline (5-10 mL) injected through the hollow-bore needle was used to hydrodissect below and then above the sciatic nerve to facilitate spread of local anesthetic following catheter insertion. The suture needle was then advanced under ultrasound guidance to an exit point approximately 6-8 cm medial to the entry site. After anesthetizing the skin at the exit point with lidocaine 1% (1-2 mL), the needle was advanced through the skin and then removed. The catheter was subsequently advanced under ultrasound visualization utilizing the echogenic markings to place the orifice directly adjacent to the sciatic nerve. Proper position of the catheter was confirmed by injection of normal saline (1-2 mL) through the catheter and visualizing spread adjacent to the nerve. The excess catheter was then cut, leaving a tail approximately 1 cm long at the exit site. The entry and exit sites were secured with clear, occlusive dressings. To facilitate tourniquet placement in the operating room, the catheter was taped up the lateral thigh and secured on the lower abdomen.

If a postoperative neurologic exam was desired by the surgeon, no local anesthetic was administered pre-operatively. In cases where no post-operative exam was anticipated, 20 mL 2% lidocaine with 5-10 µg/mL epinephrine was injected *via* the catheter immediately following placement. This was done under ultrasound visualization to confirm that the injection produced circumferential spread of the LA around the sciatic nerve. Successful block was defined as a decrease in temperature discrimination to ice after 30 minutes in the tibial nerve distribution. For cases in which the surgeon desired a postoperative exam prior to local anesthetic administration, a bolus with the same lidocaine-epinephrine volume/concentration was performed in the post-anesthesia care unit.

If the planned surgical procedure was anticipated to produce pain in the saphenous nerve distribution, a single-injection saphenous nerve block was performed with 20 mL 0.5% ropivacaine with 5-10 µg/mL epinephrine administered *via* a 17-gauge Tuohy needle under direct ultrasound visualization.

Intra-operative Procedures: Surgical anesthesia was provided with either pre-operative administration of local anesthesia as part of the nerve block combined with propofol sedation, or general anesthesia consisting of inhaled volatile anesthetic with or without nitrous oxide in oxygen with opioids provided, as needed.

Post-operative Procedures: Subjects received a 3-day perineural infusion via electronic pump (ambIT® PreSet, Summit Medical Products Inc, Salt Lake City, UT) of ropivacaine 0.2% (basal

6 mL/hour; 4 mL demand bolus; 30-minute lockout) initiated in the recovery room along with a prescription for oxycodone 5 mg tablets prior to discharge for supplementary analgesia. Subjects were contacted by telephone for 4 days following surgery to collect study outcome measures.

On the third postoperative day, subjects or their caretakers were instructed to remove the perineural catheter. Subjects were instructed to remove the occlusive dressing at the skin entry site and slowly pull out the catheter. Subjects in the suture-catheter group were specifically instructed to leave the distal dressing in place until the catheter was completely removed, thus ensuring that the small tail at the exit site was pulled through the skin prior to sterile dressing removal to avoid contamination of the catheter track.

Outcome Measures: The first four items of the Brief Pain Inventory were collected daily: worst, average, least, and current surgical pain measured using the Numeric Rating Scale (provided verbally to the investigator with specificity to the 0.1 unit). The primary outcome measure was “average” pain score on the first 2 postoperative days. Additional outcomes included daily opioid use, sleep disturbances due to pain (binary), opioid and local anesthetic infusion (e.g. perioral numbness) side effects (binary), local anesthetic leakage (binary), complete catheter dislodgement (binary), degree of sensory block (measured on a 0-10 scale with 0: no deficits and 10: completely insensate), satisfaction with postoperative analgesia (0: very dissatisfied, 10: completely satisfied), and the volume of local anesthetic consumed.

Statistical methods: We assessed the balance of randomized groups on baseline and procedural characteristics using absolute standardized difference, defined as the absolute difference in

means, mean ranks, or proportions divided by the pooled standard deviation. Baseline variables with Absolute Standardized Difference > 0.46 (i.e., $1.96 \times \sqrt{(1/n_1 + 1/n_2)}$) were considered imbalanced and were adjusted for in all analyses, as appropriate.⁹ All analyses used modified intention-to-treat such that all patients randomized and receiving at least some of the study intervention were included.

We tested noninferiority of the suture method to the through-the-needle perineural catheter method on the primary outcome of average pain score and other continuous secondary outcomes in the first 2 days after surgery using a 1-tailed noninferiority t-test at the 0.025 significance level. We used an *a priori* noninferiority delta of 1.25 for each pain score outcome and a ratio of means of 1.2 for the cumulative log-transformed opioid consumption. Noninferiority was claimed if the upper 95% confidence limit for the treatment effect (estimated from analyses described below) was less than the specified noninferiority delta. P-values were obtained from a 1-tailed t-test using a test statistic defined as $T_{NI} = (\hat{\beta} - \delta) / SE(\hat{\beta})$, where $\hat{\beta}$ is the estimated treatment effect, $SE(\hat{\beta})$ is the estimated standard error of the treatment effect, and δ is the noninferiority delta. If noninferiority was found, superiority would be tested in the same direction.

We assessed the effect of suture-method to the through-the-needle perineural catheter on each of 4 pain scores in the first 2 postoperative days using a repeated measures linear mixed effects model with an unstructured within-subject correlation structure adjusted for a variable's imbalances at baseline (age was the only imbalanced variable). The heterogeneity of the estimated treatment effect over time was assessed *via* the treatment-by-time interaction at a

significance criterion of $P < 0.15$. A significant interaction suggested that the treatment effect varies over time, in which case we estimated the treatment effect individually for each of 2 time points at the 0.0125 significance level using Bonferroni correction ($0.025/2$). Treatment effect estimates from these regression models were used to assess noninferiority of the suture versus through-the-needle methods, as described in the preceding paragraph.

For cumulative opioid consumption during the first 2 days after surgery, we first estimated the treatment effect of the suture method versus the through-the-needle method on log-transformed opioid consumption using linear regression and adjusting for age. If a patient did not receive opioids (amount = 0), 0.5 mg was added in order to facilitate the log-transformation.

We originally planned to estimate the effect of the treatment on the side effect of complete catheter dislodgment as a secondary outcome for testing noninferiority. However, we observed no event in the suture method group. Therefore, we simply compared the groups using Fisher's exact test. We also compared the randomized groups on binary outcomes using chi-square or Fisher's exact test, as appropriate.

Sample size and power estimation: The study was designed to have 90% power at the 0.025 significance level to detect noninferiority of the suture method to the through-the-needle perineural catheter on mean "average" pain score on the first 2 days following foot/ankle surgery. Assuming a noninferiority delta of 1.25 points, a standard deviation of 2.2, and a true difference of 0.5 points in the pain score favoring the suture method, a total sample size of 70

patients (35 per group) was required. SAS statistical software (Carey, NC) was used for all analyses.

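### Constant blocks of 4 at one site, with devices the operator can tell apart, make about a third of allocations deducible to someone who knows the block size and all earlier allocations; hidden, varied block sizes would cut this to about 2%

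*Combined protocol and SAP*

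**What the plan says.** The Pre-operative Procedures section describes allocation from a "computer-generated list in opaque, sealed envelopes to one of two treatments groups (1:1 ratio) in blocks of 4". It gives one block size. It mentions no variation in size and no stratification, and does not say whether the size was withheld from those enrolling patients or placing catheters. The study ran at one institution.

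Allocation comes late in the sequence: "After confirming this site was appropriate for catheter insertion, the subjects were randomized". The exclusion criteria include "Patients with nerves deeper than 5 cm from the skin surface", which also depends on imaging. Eligible patients were usually "called the night before surgery by one of the investigators to offer enrollment", and the text reports that "Only one patient who was offered enrollment in the study declined".

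The insertion paragraphs describe plainly different devices. One arm uses a Tuohy needle with a single skin entry. The other uses a curved suture needle with a second skin puncture: "The suture needle was then advanced under ultrasound guidance to an exit point approximately 6-8 cm medial to the entry site". The operator therefore knows the allocation as soon as it is used.

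Under Statistical methods, "We assessed the balance of randomized groups on baseline and procedural characteristics using absolute standardized difference", and the mixed-model paragraph reports that "age was the only imbalanced variable".

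**The concern.** Opaque sealed envelopes hide the next card. They do not hide what follows from earlier cards when the block size is known. A single unstratified sequence at one site, with an operator who cannot be masked, is the easiest setting in which to keep count.

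The envelope is opened after someone confirms that the insertion site is suitable, and no criterion for suitability is given. I infer that this leaves some discretion; the text does not say so. A person who could foresee the assignment might, at that step, leave a consented patient unrandomised. Done selectively, this would make the groups differ in expected pain for reasons other than the catheter. The baseline balance check could reveal selection on measured variables but not on unmeasured ones.

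**Working it through.** **Inputs.** 1:1 allocation in blocks of 4 (Pre-operative Procedures). Total 70, 35 per group, margin 1.25, SD 2.2, true difference 0.5 favouring suture, one-sided 0.025, power 90% (Sample size and power estimation). The documents give no predictability figure.

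**1. The plan's sample size.** The distance from the assumed truth to the margin is 1.25 + 0.5 = 1.75. The normal formula gives 2 × (1.960 + 1.282)² × 2.2² / 1.75² = 33.2, so 34 per arm. The noncentral t gives power 89.8% at 34 and 90.7% at 35 per arm, so 35 per arm (70 in total) is reproduced.

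**2. Fixed blocks of 4, size and all earlier allocations known.** The fourth allocation is always certain. The third is certain when the first two match, which has probability 1/3. That is 4/3 per block, or 33.3%. Seventy patients make 17 full blocks plus 2 patients, so the number certain is 17 + Binomial(17, 1/3):
- mean 17 + 17/3 = 22.7 (32.4%);
- possible range 17 to 34, 5th to 95th percentile 20 to 26;
- more than one third of the 70 in 33% of lists.

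The best guess is right with probability 1/2, 2/3, 2/3 and 1 at the four positions. Over 70 this is (17 × 2.833 + 1/2 + 2/3)/70 = 49.3/70 = 70.5%.

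**3. The same blocks, each earlier allocation seen with probability one half (an assumption).** Position in the block is taken as known. The fourth is certain only if both members of the pair among the first three were seen (1/4). The third is certain only if the first two match and both were seen (1/3 × 1/4 = 1/12). Total 17 × (1/4 + 1/12) = 5.7 of 70 (8.1%). Best guess 59.7%.

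**4. Block sizes 4, 6 and 8, equally likely, in random order.** The observer knows the possible sizes but not each block's size, and updates by Bayes' rule. An allocation counts as certain only if every state still possible gives the same arm. In 20,000 simulated lists with all allocations seen, 1.6 of 70 were certain (2.3%), none were certain in 55% of lists, and the best guess was right 67.8% of the time. In 2,000 lists with half seen, 0.02 of 70 were certain (0.03%) and the best-guess rate was 57.7%.

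| | Certain, all seen | Best guess, all seen | Certain, half seen | Best guess, half seen |
|---|---|---|---|---|
| Fixed blocks of 4 | 32.4% | 70.5% | 8.1% | 59.7% |
| Hidden 4/6/8 | 2.3% | 67.8% | 0.03% | 57.7% |

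**5. If each varied block's size became known.** Certain allocations per block average 4/3, 1.5 and 1.6 for sizes 4, 6 and 8. The proportion deducible would be (4/3 + 1.5 + 1.6)/18 = 24.6%. Most of the gain depends on concealing the sizes.

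**6. Cost in balance and power.** A 4/6/8 list stopped at 70 has equal groups in 72.5% of cases, a difference of 2 in 27.2% and of 4 in 0.3%. Since 70 is not a multiple of 4, the current list is equal in 66.7% and differs by 2 in 33.3%. Noncentral-t power is 90.66% at 35/35, 90.64% at 34/36 and 90.57% at 33/37.

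**7. Does the age imbalance point to selection?** No. The balance threshold is set at 1.96 standard errors, so the chance that at least one of m independent variables exceeds it is about 1 − 0.95^m: 23% for m = 5, 40% for m = 10, 64% for m = 20. The documents do not give m; 5 to 20 is assumed.

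**The case against.** The strongest objection is that the one-third figure needs one person who both knew the block size and saw every earlier allocation, and the documents show neither. They do not say who held the list, who opened envelopes, or whether one operator placed every catheter. The text is written after enrolment, so stating the block size there does not mean that enrolling staff knew it during accrual. This stands, and it is why the figure must be read as conditional. With half the allocations seen it is 8.1%.

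The opportunity was also small. Enrolment was usually offered the evening before, one person declined, the depth limit is a measurement, and randomisation followed positioning, sedation and ultrasound. Selection would have meant dropping a consented, prepared patient. This stands too, although the low refusal count does not cover patients left out after the ultrasound check, for whom no number is given.

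Someone steering patients could act on a probable guess, and there the remedy does little. Correct guesses above chance fall from 49.3 − 35 = 14.3 to about 47.5 − 35 = 12.5, roughly 13%. That is correct; what the change removes is nearly all the certain knowledge. The comparison also sets a known size against hidden sizes, so withholding them is an essential part of the remedy.

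Finally, bias from unmasked care or self-reported pain after allocation is a separate matter that block size cannot affect. That is accepted; the point here concerns selection before allocation only.

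**Conclusion.** The concern holds as a minor design weakness. Under the stated rule, an observer with full knowledge could deduce 32.4% of allocations on average. Hidden blocks of 4, 6 and 8 would reduce this to about 2.3%, while the best-guess rate would fall by only 2 to 3 percentage points. The 32.4% assumes that block size and all earlier allocations are known; the 2.3% assumes equally likely sizes that stay concealed. Nothing in the documents shows that selection took place, and the reported age imbalance is not evidence of it. No stated estimate or error rate is shown to be wrong.

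**What to change.** As a plan, generate the 1:1 list with block sizes 4, 6 and 8 in random order. Withhold the sizes from anyone who enrols patients or places catheters, and keep envelope opening after the site check. This takes one line in the list program and one sentence in the protocol. The power cost is at most about 0.1 percentage point, the sample size is unchanged, and exact balance at 70 becomes slightly more likely.

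Allocation in this trial is complete, so the list itself cannot be changed. Two sentences in the report would let readers judge whether the opening was real: whether the block size was concealed from enrolling staff and operators, and how many consented patients were not randomised after the ultrasound check.

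### The saphenous block acts on the primary pain score, but the plan states no pre-allocation record of who needs it, no stratification by it and no prespecified adjustment for it

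*Combined protocol and SAP*

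**What the plan says.** Eligibility is limited to surgery "with a planned popliteal-sciatic perineural catheter for postoperative analgesia at a single institution". Exclusion item 4 removes "Surgery outside of ipsilateral sciatic and saphenous nerve distributions (e.g., iliac crest bone graft"), so operations within the saphenous territory stay in.

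Under Pre-operative Procedures, allocation comes after the ultrasound check of the site: "After confirming this site was appropriate for catheter insertion, the subjects were randomized using a computer-generated list in opaque, sealed envelopes". The ratio is 1:1 with a block size of four, and no stratification factor is given. The two insertion techniques are described next, and the saphenous block after them: "If the planned surgical procedure was anticipated to produce pain in the saphenous nerve distribution, a single-injection saphenous nerve block was performed". The person who judges, the criterion and the time of the decision are not stated.

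No masking is described. The operator handles visibly different devices, and removal instructions differ by arm: "Subjects in the suture-catheter group were specifically instructed to leave the distal dressing in place until the catheter was completely removed".

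Under Outcome Measures, the primary outcome is the average pain rating over the first two postoperative days. It concerns pain from the operation as a whole, not pain in the sciatic territory. Under Statistical methods, balance is checked on baseline and procedural characteristics, but the adjustment rule is worded for "Baseline variables with Absolute Standardized Difference > 0.46". Age was the only variable found imbalanced, and so the only one adjusted for. Neither saphenous surgery nor the saphenous block is named in any balance check, model or sensitivity analysis.

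**The concern.** The saphenous block is a co-intervention with a direct path to the primary endpoint. It relieves pain that counts in the score but that a sciatic catheter is not meant to relieve. It is given on anticipated pain, which leaves room for judgement, and the operator knows the arm by the point at which the block is described.

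If the threshold for giving it differed between arms, even unconsciously, one arm's score would fall for a reason unrelated to catheter design. The endpoint is a subjective rating with no described masking, and the margin is 1.25 points, so a shift of a few tenths matters. Separately, planned saphenous involvement may predict pain, and with 35 patients per arm it can be unevenly spread by chance. The design does not balance it, and the analysis would adjust for it only if the imbalance passed a high threshold.

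**Working it through.** **Inputs from the plan** (Statistical methods; Sample size and power estimation): margin 1.25; SD 2.2; true difference 0.5 in favour of suture; one-sided 0.025; power 90%; 35 per group; adjustment threshold 0.46.

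**Inputs assumed**, because the documents give none: the block lowers the two-day average score by b = 1 to 2 points; block use differs between arms by d = 10 to 20 percentage points; the share with saphenous involvement is 30% to 70%, or 40% where one value is needed.

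**1. The plan's sample size.** Distance from the assumed truth to the margin: 1.25 + 0.5 = 1.75. Normal formula: n = 2 × 2.2² × (1.960 + 1.282)² / 1.75² = 33.2, so 34 per arm. With the noncentral t distribution, power is 0.898 at 34 per arm and 0.907 at 35. The stated 35 per group reproduces.

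**2. Standard error.** SE = 2.2 × √(2/35) = 0.526.

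**3. Unequal block use.** Bias = d × b. If the block is used more in the suture arm and suture is truly 1.25 points worse, the chance of claiming noninferiority is Φ(bias/SE − 1.96). If it is used more in the traditional arm, the bias works against the claim; the last column gives power at the design's assumed 0.5-point benefit (0.907 without bias).

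| d, b | Bias | Error at margin, normal | Error at margin, noncentral t | Power if pattern reversed, noncentral t |
|---|---|---|---|---|
| none | 0 | 2.5% | 2.5% | 0.907 |
| 10 points, b = 1 | 0.1 | 3.8% | 3.8% | 0.871 |
| 10 points, b = 2; or 20 points, b = 1 | 0.2 | 5.7% | 5.6% | 0.828 |
| 20 points, b = 2 | 0.4 | 11.5% | 11.3% | 0.716 |

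**4. What the 0.46 rule lets through.** For a yes/no variable with prevalence p, the standardized difference is gap / √(p(1 − p)), so the largest gap that escapes adjustment is 0.46 × √(p(1 − p)):

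- p = 0.3 or 0.7: 0.46 × 0.458 = 0.21
- p = 0.5: 0.46 × 0.5 = 0.23

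A gap of 21 to 23 percentage points in planned involvement would pass unadjusted. The block itself comes after allocation in the described sequence, and the rule as worded covers baseline variables only.

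**5. Gain from prespecified adjustment.** If involvement shifts pain by 1 point at a 40% share, it explains 0.4 × 0.6 × 1² = 0.24 of the variance of 2.2² = 4.84. The residual SD is √4.60 = 2.145. With one degree of freedom spent (67 left), power rises from 0.907 to 0.920.

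**The case against.** The strongest reply is that the trigger is the planned procedure, which is known before the envelope is opened, and that item 4 already makes staff judge surgical territory at screening. The order of the text may show when the block was given, not when it was decided. One rule is stated for both arms, and no reason is given why an operator would favour either. This stands to the extent that a late decision is only an inference from silence. It does not close the gap, because no pre-allocation record is stated and such a record is what would settle the matter.

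Second, planned saphenous surgery is a pre-randomization trait. Randomization balances it in expectation, and chance imbalance is already within the nominal error rate. That is correct: involvement by itself causes no systematic bias. The case for stratifying and adjusting rests on precision and on having a fixed classification against which actual block use can be compared.

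Third, procedural characteristics were checked for balance, and the variables are not listed, so saphenous involvement may have been among them. That is possible, but the threshold would still have let a sizeable gap through.

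A reader might also infer that saphenous pain dilutes the catheter difference and so inflates false noninferiority claims. The documents do not support this. The stated target is mean pain after foot or ankle surgery in the enrolled population, so a smaller difference in that population is the quantity being tested. Under the design's own assumption of a 0.5-point benefit, dilution lowers the chance of a claim: if catheter effects are halved in 30% to 50% of patients, the difference becomes −0.425 to −0.375 and power falls from about 0.91 to 0.88–0.86.

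**Conclusion.** The point holds as a gap in design and analysis. A discretionary co-intervention acts on a subjective primary endpoint with no described masking, and the plan states no pre-allocation record, no stratification and no prespecified adjustment for it. Under the assumed block effect of 1 to 2 points and excess use of 10 to 20 percentage points in the suture arm, the error rate at the margin is about 3.8% to 11.5% instead of 2.5%. The reverse pattern would cut power from 0.907 to between 0.871 and 0.716. The block effect and the gap in use are both assumptions.

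It would be tempting to conclude that the trial is biased toward noninferiority. The documents do not support that: the direction depends on which arm received more blocks, no figure for block use is given, and nothing shows that use differed or that any decision was made after allocation. This is a cheap improvement, not a demonstrated flaw in the result.

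**What to change.** In the design: record planned saphenous involvement (yes/no) from the planned procedure before the envelope is opened, and log any later change as a deviation. Stratify the envelopes by it. Include it as a prespecified factor in the primary pain model, whatever the observed imbalance.

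The text describes conduct in the past tense. If randomization is complete, have existing staff who do not know the arm classify involvement from the planned procedure, and add it to the primary model as a sensitivity analysis. State who made the original judgement and when.

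In either case, report block use by arm, preferably within each level of planned involvement, because adjusting for the plan does not correct for blocks given unequally to patients with the same plan. Give the estimate and interval in sciatic-only surgery as descriptive support; the noninferiority conclusion should not depend on it.

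The cost is one tick-box, a second envelope set with slightly more handling, one model degree of freedom and a small table. No change to who receives the block is proposed.

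### When the two days are analysed separately, the noninferiority claim rule still names a 95% limit although each day is tested at one-sided 0.0125

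*Combined protocol and SAP*

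**What the plan says.** All the relevant text is in the combined protocol and SAP, under Statistical methods.

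- The noninferiority paragraph tests the primary outcome "using a 1-tailed noninferiority t-test at the 0.025 significance level", with a "noninferiority delta of 1.25 for each pain score outcome".
- The same paragraph gives the only criterion for a claim: "Noninferiority was claimed if the upper 95% confidence limit for the treatment effect" is less than delta. A parenthesis applies this to the estimates from the analyses described afterwards. The paragraph also defines a one-tailed P-value from (estimate − delta)/SE.
- The next paragraph, on the repeated measures model, covers a treatment-by-time interaction with P < 0.15, "in which case we estimated the treatment effect individually for each of 2 time points at the 0.0125 significance level using Bonferroni correction", that is, 0.025/2.
- That paragraph ends by saying that the model estimates were "used to assess noninferiority of the suture versus through-the-needle methods, as described in the preceding paragraph". The paragraph referred to is the one with the 95% rule.

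No other confidence level is named for a noninferiority claim. The plan does not say whether one day or both must pass.

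**The concern.** In the day-specific branch the plan names two thresholds for one decision. The test level is one-sided 0.0125. The claim rule is a 95% limit, which corresponds to one-sided 0.025. Two analysts who follow the text could reach opposite verdicts from the same estimate and standard error, one using the interval and the other the P-value. The branch would then decide the primary conclusion, because the primary outcome is average pain over these same two days. If the interval governs, each day is judged at twice the intended level.

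**Working it through.** **Inputs.** Margin 1.25 and one-sided 0.025 (Statistical methods); 0.0125 per day after an interaction with P < 0.15 (Statistical methods, repeated measures paragraph); SD 2.2, true difference 0.5 favouring suture, 35 per group and 90% power (Sample size and power estimation). The documents give neither a daily SD nor a between-day correlation. I take 2.2 as the daily SD and show a range for the correlation.

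**1. The plan's own figure.** The distance from the assumed truth to the margin is 1.25 + 0.5 = 1.75. The normal approximation gives n per group = 2 × 2.2² × (1.960 + 1.282)² / 1.75² = 33.2, so 34. The noncentral t calculation gives 35 per group, with 90.7% power. The stated total of 70 is reproduced at one-sided 0.025. One-sided 0.05 would need only 28 per group.

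**2. Cut-offs for a claim.** SE = 2.2 × √(2/35) = 0.526, with 70 − 2 = 68 degrees of freedom. A claim requires estimate < 1.25 − t × SE.

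| Rule | t | Half-width | Estimate must be below |
|---|---|---|---|
| Upper limit, two-sided 95% CI (one-sided 0.025) | 1.995 | 1.049 | 0.201 |
| Upper limit, two-sided 97.5% CI (one-sided 0.0125) | 2.292 | 1.205 | 0.045 |

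**3. Two-day effect.** The 95% limit and the one-sided 0.025 test use the same t quantile, so they always agree.

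**4. Day-specific effect.** Estimates between 0.045 and 0.201 pass the 95% limit and fail the 0.0125 test. Take an estimate of 0.10. The 95% upper limit is 0.10 + 1.049 = 1.149, below 1.25, so noninferiority is claimed. The test statistic is (0.10 − 1.25)/0.526 = −2.19, which does not reach −2.292, so the test does not reject.

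**5. How often.** For a single day, the chance of an estimate in this window is 90.7% − 84.7% = 6.0% at the design difference, about 11% at a true difference of 0, and 2.5% − 1.25% = 1.25% at the margin. The branch must also be entered. With no true interaction that happens 15% of the time. At the design difference, the chance of entering the branch and having at least one day in the window is about 2% (correlation 0.3 to 0.7).

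**6. Error rate of the whole procedure.** Simulation with both days at the margin, normal approximation, equal daily variances, and a claim on either day counted:

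| Between-day correlation | 95% limit per day | 0.0125 per day |
|---|---|---|
| 0.5 | 4.0% | 3.2% |
| 0.7 | 3.5% | 2.9% |

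The two-day branch contributes 0.85 × 2.5% = 2.1% in every cell, because under equal variances the interaction contrast is independent of the two-day mean. The day-specific branch supplies the rest: 4.0 − 2.1 = 1.9 against 3.2 − 2.1 = 1.1 points at correlation 0.5, and 3.5 − 2.1 = 1.4 against 2.9 − 2.1 = 0.8 points at 0.7. The choice of confidence level therefore accounts for 0.6 to 0.8 points.

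**The case against.** The strongest reply is that the text should be read as a whole. The 0.0125 sentence is specific to the daily analyses and follows the general rule. The back-reference brings in the whole noninferiority procedure, including the margin, the test statistic and the P-value, so the natural reading is the same procedure at the corrected level. Otherwise the correction would have no purpose. As an account of intent this is plausible, and it is why one should not conclude that the Bonferroni correction was meant to have no effect on the claim. It does not settle the wording: the rule referred to names 95%, and no 97.5% limit appears.

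A second reply is that if both days must pass, the joint error is at most 0.025 even with 95% limits. That is true, but the plan states no such rule, and halving alpha is the correction for separate claims. Even then the written interval and test levels would differ.

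Two stronger readings are tempting and do not stand. A reader might take the 95% limit as a one-sided bound and infer a conflict with 0.025 for the two-day effect as well. By ordinary convention it is the upper limit of a two-sided interval, the adjacent sentence gives 0.025, and the sample size fits 0.025. A reader might also take the chance of at least one false claim over two tests, 4.2% to 4.5% at 95% limits (correlation 0.7 to 0.5), as the trial's error rate. That treats the daily tests as always performed, whereas they run only after an interaction with P < 0.15.

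**Conclusion.** The claim rule and the test level are inconsistent as written, in the day-specific branch only. The nominal per-day level under the literal rule is 2.5% instead of 1.25%, and the two rules disagree for estimates from 0.045 to 0.201, a band 0.156 points wide. The effect on the overall false-claim rate is under one percentage point. It rests on a daily SD of 2.2, 35 per group, no gain from covariate adjustment, an assumed between-day correlation of 0.5 to 0.7, and counting a claim on either day.

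Correcting the level should not be presented as restoring 0.025 overall: the remaining 2.9% to 3.2% comes from choosing the analysis by an interaction pretest, which is a separate matter. The documents do not say whether the branch was entered, so nothing here shows that a conclusion changed. This is a minor point.

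**What to change.** Replace the claim sentence with: noninferiority is claimed if the upper limit of the two-sided 95% confidence interval (two-day effect, one-sided 0.025) or of the two-sided 97.5% confidence interval (each day-specific effect, one-sided 0.0125) is below delta. Report those intervals. State also whether a claim on either day counts or both days must pass, since the error rate depends on it.

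The cost is one sentence and one alpha option in the model code. Margin, overall alpha and data collection are unchanged. The day-specific intervals become slightly wider: the half-width rises from 1.049 to 1.205 under the design assumptions. Per-day power at the design difference is then 84.7% instead of 90.7%, which the stated 0.0125 test already implies.
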